Appendix A

K57.31	(ICD10) Diverticulosis of large intestine without perforation or abscess with bleeding
K57.33	(ICD10) Diverticulitis of large intestine without perforation or abscess with bleeding
K57.41	(ICD10) Diverticulitis of both small and large intestine with perforation and abscess with bleeding
K57.51	(ICD10) Diverticulosis of both small and large intestine without perforation or abscess with bleeding
K57.53	(ICD10) Diverticulitis of both small and large intestine without perforation or abscess with bleeding
K57.81	(ICD10) Diverticulitis of intestine, part unspecified, with perforation and abscess with bleeding
K57.91	(ICD10) Diverticulosis of intestine, part unspecified, without perforation or abscess with bleeding
K57.93	(ICD10) Diverticulitis of intestine, part unspecified, without perforation or abscess with bleeding
K62.5	(ICD10) Hemorrhage of anus and rectum
K63.1	(ICD10) Perforation of intestine (nontraumatic)
K63.81	(ICD10) Dieulafoy lesion of intestine
K66.1	(ICD10) Hemoperitoneum
K92.0	(ICD10) Hematemesis
K92.1	(ICD10) Melena
K92.2	(ICD10) Gastrointestinal hemorrhage, unspecified
M25.00	(ICD10) Hemarthrosis, unspecified joint
M25.011	(ICD10) Hemarthrosis, right shoulder
M25.012	(ICD10) Hemarthrosis, left shoulder
M25.019	(ICD10) Hemarthrosis, unspecified shoulder
M25.021	(ICD10) Hemarthrosis, right elbow
M25.022	(ICD10) Hemarthrosis, left elbow
M25.029	(ICD10) Hemarthrosis, unspecified elbow
M25.031	(ICD10) Hemarthrosis, right wrist
M25.032	(ICD10) Hemarthrosis, left wrist
M25.039	(ICD10) Hemarthrosis, unspecified wrist
M25.041	(ICD10) Hemarthrosis, right hand
M25.042	(ICD10) Hemarthrosis, left hand
M25.049	(ICD10) Hemarthrosis, unspecified hand
M25.051	(ICD10) Hemarthrosis, right hip
M25.052	(ICD10) Hemarthrosis, left hip
M25.059	(ICD10) Hemarthrosis, unspecified hip
M25.061	(ICD10) Hemarthrosis, right knee
M25.062	(ICD10) Hemarthrosis, left knee

Appendix A

M25.069	(ICD10) Hemarthrosis, unspecified knee
M25.071	(ICD10) Hemarthrosis, right ankle
M25.072	(ICD10) Hemarthrosis, left ankle
M25.073	(ICD10) Hemarthrosis, unspecified ankle
M25.074	(ICD10) Hemarthrosis, right foot
M25.075	(ICD10) Hemarthrosis, left foot
M25.076	(ICD10) Hemarthrosis, unspecified foot
M25.08	(ICD10) Hemarthrosis, other specified site
R58	(ICD10) Hemorrhage, not elsewhere classified
R04	(ICD10) Hemorrhage from respiratory passages
R04.0	(ICD10) Epistaxis
R04.1	(ICD10) Hemorrhage from throat
R04.2	(ICD10) Hemoptysis
R04.8	(ICD10) Hemorrhage from other sites in respiratory passages
R04.81	(ICD10) Acute idiopathic pulmonary hemorrhage in infants
R04.89	(ICD10) Hemorrhage from other sites in respiratory passages
R04.9	(ICD10) Hemorrhage from respiratory passages, unspecified
R31	(ICD10) Hematuria
R31.0	(ICD10) Gross hematuria
R31.1	(ICD10) Benign essential microscopic hematuria
R31.2	(ICD10) Other microscopic hematuria
R31.21	(ICD10) Asymptomatic microscopic hematuria
R31.29	(ICD10) Other microscopic hematuria
R31.9	(ICD10) Hematuria, unspecified
Px inpatient any position	
44.43	(ICD9) ENDOSCOPIC CONTROL OF GASTRIC OR DUODENAL BLEEDING
0W3P8ZZ	(ICD10) Control Bleeding in Gastrointestinal Tract, Via Natural or Artificial Opening Endoscopic
43255	(HCPCS) Esophagogastroduodenoscopy, flexible, transoral; with control of bleeding, any method / Upper gastrointestinal endoscopy including esophagus, stomach, and either the duodenum and/or jejunum as appropriate; with control of bleeding, any method

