1.5 Secondary endpoint for replication (assay sensitivity) and RCT finding

Major bleeding; RR = 0.90 (95% CI 0.76–1.07)

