6.3.1 Outcome variables

Primary Effectiveness outcomes of interest: (definitions provided in **Appendix A**):

- **Primary Outcome:** VTE

Safety outcomes of interest:

1. Major bleeding

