Appendix A

Title

Venous Thromboembolism (VTE)

ICD-9 Dx inpatient primary position

PE

- 415.1 PULMONARY EMBOLISM AND INFARCTION
- 415.11 IATROGENIC PULMONARY EMBOLISM AND INFARCTION
- 415.19 OTHER PULMONARY EMBOLISM AND INFARCTION

DVT

- 451.1 PHLEBITIS AND THROMBOPHLEBITIS OF DEEP VEINS OF LOWER EXTREMITIES
- 451.11 PHLEBITIS AND THROMBOPHLEBITIS OF FEMORAL VEIN (DEEP) (SUPERFICIAL)
- 451.19 PHLEBITIS AND THROMBOPHLEBITIS OF OTHER
- 451.2 PHLEBITIS AND THROMBOPHLEBITIS OF LOWER EXTREMITIES UNSPECIFIED
- 451.81 PHLEBITIS AND THROMBOPHLEBITIS OF ILIAC VEIN
- 451.9 PHLEBITIS AND THROMBOPHLEBITIS OF UNSPECIFIED SITE
- 453 BUDD-CHIARI SYNDROME
- 453.1 THROMBOPHLEBITIS MIGRANS
- 453.2 EMBOLISM AND THROMBOSIS OF INFERIOR VENA CAVA
- 453.4 ACUTE VENOUS EMBOLISM AND THROMBOSIS OF DEEP VESSELS OF LOWER EXTREMITY
- 453.4 ACUTE VENOUS EMBOLISM AND THROMBOSIS OF UNSPECIFIED DEEP VESSELS OF LOWER EXTREMITY
- 453.41 ACUTE VENOUS EMBOLISM AND THROMBOSIS OF DEEP VESSELS OF PROXIMAL LOWER EXTREMITY
- 453.42 ACUTE VENOUS EMBOLISM AND THROMBOSIS OF DEEP VESSELS OF DISTAL LOWER EXTREMITY
- 453.5 CHRONIC VENOUS EMBOLISM AND THROMBOSIS OF DEEP VESSELS OF LOWER EXTREMITY
- 453.5 CHRONIC VENOUS EMBOLISM AND THROMBOSIS OF UNSPECIFIED DEEP VESSELS OF LOWER EXTREMITY
- 453.51 CHRONIC VENOUS EMBOLISM AND THROMBOSIS OF DEEP VESSELS OF PROXIMAL LOWER EXTREMITY
- 453.52 CHRONIC VENOUS EMBOLISM AND THROMBOSIS OF DEEP VESSELS OF DISTAL LOWER EXTREMITY
- 453.8 ACUTE VENOUS EMBOLISM AND THROMBOSIS OF OTHER SPECIFIED VEINS
- 453.82 ACUTE VENOUS EMBOLISM AND THROMBOSIS OF DEEP VEINS OF UPPER EXTREMITY
- 453.83 ACUTE VENOUS EMBOLISM AND THROMBOSIS OF UPPER EXTREMITY UNSPECIFIED
- 453.84 ACUTE VENOUS EMBOLISM AND THROMBOSIS OF AXILLARY VEINS
- 453.85 ACUTE VENOUS EMBOLISM AND THROMBOSIS OF SUBCLAVIAN VEINS
- 453.86 ACUTE VENOUS EMBOLISM AND THROMBOSIS OF INTERNAL JUGULAR VEINS
- 453.87 ACUTE VENOUS EMBOLISM AND THROMBOSIS OF OTHER THORACIC VEINS
- 453.89 ACUTE VENOUS EMBOLISM AND THROMBOSIS OF OTHER SPECIFIED VEINS

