Appendix A

Title

Major Bleeding

ICD-9 Dx inpatient any position

423	(ICD9) HEMOPERICARDIUM
430	(ICD9) SUBARACHNOID HEMORRHAGE
431	(ICD9) INTRACEREBRAL HEMORRHAGE
432	(ICD9) NONTRAUMATIC EXTRADURAL HEMORRHAGE
432.1	(ICD9) SUBDURAL HEMORRHAGE
432.9	(ICD9) UNSPECIFIED INTRACRANIAL HEMORRHAGE
459	(ICD9) HEMORRHAGE UNSPECIFIED
531	(ICD9) ACUTE GASTRIC ULCER WITH HEMORRHAGE
531	(ICD9) ACUTE GASTRIC ULCER WITH HEMORRHAGE WITHOUT OBSTRUCTION
531.01	(ICD9) ACUTE GASTRIC ULCER WITH HEMORRHAGE WITH OBSTRUCTION
531.2	(ICD9) ACUTE GASTRIC ULCER WITH HEMORRHAGE AND PERFORATION
531.2	(ICD9) ACUTE GASTRIC ULCER WITH HEMORRHAGE AND PERFORATION WITHOUT OBSTRUCTION
531.21	(ICD9) ACUTE GASTRIC ULCER WITH HEMORRHAGE AND PERFORATION WITH OBSTRUCTION
531.4	(ICD9) CHRONIC OR UNSPECIFIED GASTRIC ULCER WITH HEMORRHAGE
531.4	(ICD9) CHRONIC OR UNSPECIFIED GASTRIC ULCER WITH HEMORRHAGE WITHOUT OBSTRUCTION
531.41	(ICD9) CHRONIC OR UNSPECIFIED GASTRIC ULCER WITH HEMORRHAGE WITH OBSTRUCTION
531.6	(ICD9) CHRONIC OR UNSPECIFIED GASTRIC ULCER WITH HEMORRHAGE AND PERFORATION
531.6	(ICD9) CHRONIC OR UNSPECIFIED GASTRIC ULCER WITH HEMORRHAGE AND PERFORATION WITHOUT OBSTRUCTION
531.61	(ICD9) CHRONIC OR UNSPECIFIED GASTRIC ULCER WITH HEMORRHAGE AND PERFORATION WITH OBSTRUCTION
532	(ICD9) ACUTE DUODENAL ULCER WITH HEMORRHAGE
532	(ICD9) ACUTE DUODENAL ULCER WITH HEMORRHAGE WITHOUT OBSTRUCTION
532.01	(ICD9) ACUTE DUODENAL ULCER WITH HEMORRHAGE WITH OBSTRUCTION
532.2	(ICD9) ACUTE DUODENAL ULCER WITH HEMORRHAGE AND PERFORATION
532.2	(ICD9) ACUTE DUODENAL ULCER WITH HEMORRHAGE AND PERFORATION WITHOUT OBSTRUCTION
532.21	(ICD9) ACUTE DUODENAL ULCER WITH HEMORRHAGE AND PERFORATION WITH OBSTRUCTION
532.4	(ICD9) CHRONIC OR UNSPECIFIED DUODENAL ULCER WITH HEMORRHAGE
532.4	(ICD9) CHRONIC OR UNSPECIFIED DUODENAL ULCER WITH HEMORRHAGE WITHOUT OBSTRUCTION

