Appendix A

599.7	(ICD9) HEMATURIA
599.7	(ICD9) HEMATURIA UNSPECIFIED
599.71	(ICD9) GROSS HEMATURIA
599.72	(ICD9) MICROSCOPIC HEMATURIA
786.3	(ICD9) HEMOPTYSIS
786.3	(ICD9) HEMOPTYSIS UNSPECIFIED
786.31	(ICD9) ACUTE IDIOPATHIC PULMONARY HEMORRHAGE IN INFANTS
786.39	(ICD9) OTHER HEMOPTYSIS

ICD-10 Dx inpatient any position

I31.2	(ICD10) Hemopericardium, not elsewhere classified
I60.00	(ICD10) Nontraumatic subarachnoid hemorrhage from unspecified carotid siphon and bifurcation
I60.01	(ICD10) Nontraumatic subarachnoid hemorrhage from right carotid siphon and bifurcation
I60.02	(ICD10) Nontraumatic subarachnoid hemorrhage from left carotid siphon and bifurcation
I60.10	(ICD10) Nontraumatic subarachnoid hemorrhage from unspecified middle cerebral artery
I60.11	(ICD10) Nontraumatic subarachnoid hemorrhage from right middle cerebral artery
I60.12	(ICD10) Nontraumatic subarachnoid hemorrhage from left middle cerebral artery
I60.2	(ICD10) Nontraumatic subarachnoid hemorrhage from anterior communicating artery
I60.30	(ICD10) Nontraumatic subarachnoid hemorrhage from unspecified posterior communicating artery
I60.31	(ICD10) Nontraumatic subarachnoid hemorrhage from right posterior communicating artery
I60.32	(ICD10) Nontraumatic subarachnoid hemorrhage from left posterior communicating artery
I60.4	(ICD10) Nontraumatic subarachnoid hemorrhage from basilar artery
I60.50	(ICD10) Nontraumatic subarachnoid hemorrhage from unspecified vertebral artery
I60.51	(ICD10) Nontraumatic subarachnoid hemorrhage from right vertebral artery
I60.52	(ICD10) Nontraumatic subarachnoid hemorrhage from left vertebral artery
I60.6	(ICD10) Nontraumatic subarachnoid hemorrhage from other intracranial arteries
I60.7	(ICD10) Nontraumatic subarachnoid hemorrhage from unspecified intracranial artery
I60.8	(ICD10) Other nontraumatic subarachnoid hemorrhage
I60.9	(ICD10) Nontraumatic subarachnoid hemorrhage, unspecified
I61.0	(ICD10) Nontraumatic intracerebral hemorrhage in hemisphere, subcortical
I61.1	(ICD10) Nontraumatic intracerebral hemorrhage in hemisphere, cortical
I61.2	(ICD10) Nontraumatic intracerebral hemorrhage in hemisphere, unspecified
I61.3	(ICD10) Nontraumatic intracerebral hemorrhage in brain stem

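### The major-bleeding list counts microscopic and asymptomatic hematuria, epistaxis and hemoptysis from any inpatient position with no severity criterion, which lowers the specificity of the only safety outcome and can bias its hazard ratio

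*Combined protocol and SAP*

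**What the plan says.** Section 6.3.1 lists one item, major bleeding, under "Safety outcomes of interest" and leaves its definition to Appendix A. Section 1.5 makes the same outcome the secondary endpoint for replication, with a trial ratio of 0.90 (95% CI 0.76 to 1.07).

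In Appendix A the bleeding diagnoses fall under two rules, "ICD-9 Dx inpatient any position" and "ICD-10 Dx inpatient any position". The accepted codes include:

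- **Hematuria:** 599.72 ("MICROSCOPIC HEMATURIA"), R31.1 ("Benign essential microscopic hematuria"), R31.21 ("Asymptomatic microscopic hematuria"), and R31.2 and R31.29 (other microscopic hematuria).
- **Epistaxis:** 784.7 and R04.0.
- **Hemoptysis:** 786.3, 786.39 and R04.2.

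None of these codes carries a further condition such as primary position, transfusion, a fall in hemoglobin or a critical site. The VTE outcome in the same appendix is stricter: its ICD-9 heading reads "ICD-9 Dx inpatient primary position", and the ICD-10 heading applies the same rule.

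**The concern.** A finding labelled microscopic, benign or asymptomatic is not major on its face. Under the list as written, a patient admitted for something else, with such a finding among the secondary diagnoses, has had a major bleed.

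Hemoptysis raises a second problem. A stay with PE as the primary diagnosis and hemoptysis as a secondary one meets both the VTE and the bleeding definition, so an efficacy failure also enters the safety analysis as a harm.

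The stake is the use of this endpoint in a replication. Events that reflect admission and coding more than serious bleeding make the bleeding ratio harder to compare with the trial's. The primary VTE analysis is not affected.

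**Working it through.** **1. The code rules side by side**

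| | VTE | Major bleeding |
|---|---|---|
| Setting | inpatient | inpatient |
| Diagnosis position | primary only | any |
| Severity condition on the codes in question | not applicable | none |

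The overlap follows from these rules alone: I26.99 primary with R04.2 secondary satisfies both columns. Outpatient codes do not count.

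**2. The benchmark in Section 1.5**

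The plan gives no count, rate or power for bleeding in the claims data; its power tables concern VTE. The only bleeding figure is the trial's 0.90 (0.76 to 1.07).

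- Consistency: √(0.76 × 1.07) = 0.902, which agrees with 0.90.
- Standard error of the log ratio: ln(1.07/0.76) / (2 × 1.96) = 0.0873.
- Implied events under 1:1 allocation (Appendix A: 2,419 of 4,832 exposed): 4 / 0.0873² ≈ 525, or 525/4,832 ≈ 11% of patients. Rounding of the limits gives 492 to 561.
- Read as a simple risk ratio: 4 / (0.0873² + 4/4,832) ≈ 474, or about 10%.
- For comparison, the VTE result in Appendix A, 1.12 (0.75 to 1.68): the standard error is ln(1.68/0.75)/3.92 = 0.2057, and 4/0.2057² ≈ 95 events, or 2.0%.

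The figure labelled major bleeding thus rests on about 5.5 times as many events as recurrent VTE (525/95). It may describe a broader bleeding outcome; the documents do not say.

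**3. Possible bias**

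Let f be the share of counted reference-group events that are not major bleeds. Then

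HR_observed = (1 − f) × HR_true + f × HR_extra.

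The documents give neither f nor HR_extra, so both are assumed. HR_true is set to the protocol's 0.90, taken at its label.

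| Assumption on the extra events | f = 0.20 | f = 0.50 |
|---|---|---|
| Unrelated to treatment (HR_extra = 1.00) | 0.8 × 0.90 + 0.2 × 1.00 = 0.92 | 0.5 × 0.90 + 0.5 × 1.00 = 0.95 |
| Follow recurrent VTE (HR_extra = 1.12) | 0.8 × 0.90 + 0.2 × 1.12 = 0.944 | 0.5 × 0.90 + 0.5 × 1.12 = 1.01 |
| Share the drug effect (HR_extra = 0.90) | 0.90 | 0.90 |

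In the second row the estimate passes 1 only when f exceeds (1 − 0.90)/(1.12 − 0.90) = 0.45.

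A stronger true effect would be pulled further. With HR_true = 0.70, a value found in neither the protocol nor its appendices, and HR_extra = 1.00, the results are 0.76 and 0.85.

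**The case against.** The strongest reply has four parts.

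**Dilution is assumed.** It comes from setting the ratio for the extra events to 1. If hematuria and epistaxis on an anticoagulant respond to the drug as major bleeds do, there is no dilution at any f. This stands. A reader might infer that the list is shown to dilute the contrast, or that the endpoint cannot discriminate between the drugs. The documents support neither: they give no bleeding counts by code, and at their own 0.90 the illustrated shift of 0.02 to 0.05 lies well inside the trial's interval.

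**The benchmark may itself be broad.** With about 525 implied events, a narrow list could move away from the quantity being replicated. This stands as a reason to identify the benchmark. It does not make asymptomatic or microscopic hematuria a major bleed: either the list or the label is wrong.

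**Primary position has its own reason for VTE.** Practically every patient has a baseline PE code (Appendix B), so secondary VTE codes may carry over the index event. That reason does not transfer to bleeding. A primary-position rule for every hematuria, epistaxis and hemoptysis code would also drop secondary-position gross hematuria (599.71, R31.0), whose label does not exclude a serious bleed. This stands, so that rule belongs in a sensitivity analysis.

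**Nothing is counted twice within one analysis.** VTE and bleeding are analysed separately, each to its first event (Section 6.3.2). This is correct, but one PE stay can still supply the event in both analyses. How often hemoptysis accompanies PE is a clinical matter that the documents do not address.

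The infant pulmonary-hemorrhage codes (786.31, R04.81) are out of place, but removing them should change nothing in a cohort with an age exclusion and mean ages of about 54 to 75.

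**Conclusion.** The point holds as a specificity defect in the plan's only safety outcome. Five hematuria codes contradict the outcome's name by their own labels. Epistaxis and hemoptysis are accepted from any inpatient position without a severity criterion, and one stay can meet both outcome definitions.

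The effect on the hazard ratio is possible, not demonstrated. At the protocol's 0.90, with an assumed 20–50% of reference events unrelated to treatment, it is a move to 0.92–0.95. Passing 1 would need about 45% or more of reference events to behave like recurrent VTE, a share for which the documents give no evidence. With a shared drug effect the bias is nil. These figures take 0.90 to be the major-bleeding ratio, which the implied event count puts in some doubt.

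The change should be made, since the list, the label and the benchmark do not clearly describe the same outcome.

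**What to change.** Sections 13.1 and 13.2 are still blank, so all of this can be fixed before the comparative analysis:

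1. Delete 599.72, R31.1, R31.2, R31.21 and R31.29 from the primary bleeding list.
2. Do not count a hemoptysis code on a claim whose primary diagnosis is a listed PE code.
3. Pre-specify two sensitivity analyses in Section 13.2: (a) the current list; (b) a version requiring primary position for the remaining hematuria, epistaxis, throat-bleeding and hemoptysis codes.
4. State in Section 1.5 which trial bleeding endpoint the 0.90 (0.76 to 1.07) represents, and reconcile the label in Sections 1.5 and 6.3.1 with the list.

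The cost is a code-list edit, fewer bleeding events and somewhat wider intervals. Losing a share f of events widens the log-scale interval by a factor of about 1/√(1 − f): 12% at f = 0.20 and 41% at f = 0.50. Those shares are illustrative. The loss from steps 1 and 2 cannot be known until events are tabulated by code, which can be done pooled over treatment groups.

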Appendix A

Title

Pregnancy

ICD-9 Dx inpatient any position

- 650 Normal delivery
- 660 Obstructed labor
- 661 Abnormality of forces of labor
- 662 Long labor
- 663 Umbilical cord complications during labor and delivery
- 664 Trauma to perineum and vulva during delivery
- 665 Other obstetrical trauma
- 667 Retained placenta or membranes without hemorrhage
- 668 Complications of the administration of anesthetic or other sedation in labor and delivery
- 669.94 Unspecified complication of labor and delivery postpartum condition or complication
- V24 Postpartum care and examination
- V24.0 Postpartum care and examination immediately after delivery
- V24.1 Postpartum care and examination of lactating mother
- V24.2 Routine postpartum follow
- V27 Outcome of delivery
- V27.0 Mother with single liveborn
- V27.1 Mother with single stillborn
- V27.2 Mother with twins both liveborn
- V27.3 Mother with twins one liveborn and one stillborn
- V27.4 Mother with twins both stillborn
- V27.5 Mother with other multiple birth all liveborn
- V27.6 Mother with other multiple birth some liveborn
- V27.7 Mother with other multiple birth all stillborn
- V27.9 Mother with unspecified outcome of delivery

ICD-9 Px inpatient any position

- 72.0 Low forceps operation
- 72.1 Low forceps operation with episiotomy
- 72.2 Mid forceps operation
- 72.21 Mid forceps operation with episiotomy
- 72.29 Other mid forceps operation

[figure not shown]

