5.2.1 Eligible cohort entry dates

Market availability of rivaroxaban in the U.S. prevention of venous thromboembolism after orthopedic surgery started on July 01, 2011

- For Medicare: July 01, 2011– December 31, 2017 (end of available data)
- For Marketscan: July 01, 2011 – December 31, 2018 (end of available data)
- For Optum: July 01, 2011 – March 31, 2020 (end of available data)

5.2.2 Specify inclusion/exclusion criteria for cohort entry and define the index date.

Inclusion and exclusion criteria were adapted from the trial as closely as possible. Definitions for all inclusion/exclusion are provided in **Appendix A** and are summarized in the flowcharts below.

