5.3 Flowchart of the study cohort assembly

	Optum		Truven		Medicare	
	Less Excluded Patients	Remaining Patients	Less Excluded Patients	Remaining Patients	Less Excluded Patients	Remaining Patients
All patients		78,202,636		200,203,908		6,886,908
Did not meet cohort entry criteria	-77,207,180	995,456	-199,008,369	1,195,539	-1,964,276	4,922,632

Excluded due to insufficient enrollment	-127,407	868,049	-98,795	1,096,744	-1,580,438	3,342,194
Excluded due to prior use of referent	-508,219	359,830	-676,683	420,061	-2,158,638	1,183,556
Excluded due to prior use of exposure and because patient qualified in >1 exposure category	-216,850	142,980	-210,419	209,642	-680,443	503,113
Excluded based on Age < 65 (Medicare only)	-	-	-	-	-55358	447,755
Excluded based on Age, Gender, and Use of other NOACs (dabigatran, apixaban, edoxaban)	-5393	137,587	-4262	205,380	-17641	430,114
Excluded based on Inclusion 1 - Pulmonary embolism	-117,221	20,366	-169,963	35,417	-372,047	58,067
Excluded based on Exclusion 1 - Age and Exclusion 2 - Thrombectomy or insertion of a caval filter	-196	20,170	-274	35,143	-546	57,521
Excluded based on Exclusion 3 - Other Indications for VKA	-1836	18,334	-1,617	33,526	-6,213	51,308
Excluded based on Exclusion 6 - KD stage 4/5/ESRD	-56	18,278	-42	33,484	-136	51,172
Excluded based on Exclusion 7 - Significant liver disease	-426	17,852	-505	32,979	-900	50,272
Excluded based on Exclusion 8 - Bacterial endocarditis and Exclusion 9 - CCI >= 10	-154	17,698	-114	32,865	-398	49,874
Excluded based on Exclusion 10 - Active bleeding or high risk for bleeding	-262	17,436	-334	32,531	-670	49,204
Excluded based on Exclusion 11 - malignant hypertension	-33	17,403	-42	32,489	-57	49,147
Excluded based on Exclusion 12 - Pregnancy and Exclusion 14 - strong CYP3A4 inhibitors or strong CYP3A4 inducers	-19	17,384	-44	32,445	-29	49,118
Final cohort		17,384		32,445		49,118

6. Variables

6.1 Exposure-related variables:

Study drug:

The study exposure of interest is initiation of rivaroxaban. New initiation will be defined by no use of rivaroxaban or warfarin in the prior 6 months before treatment initiation (washout period).

Comparator:

New initiators of warfarin, defined by no use of rivaroxaban or warfarin in the prior 6 months.

6.2 Covariates:

- Age
- Sex
- Combined Comorbidity Index (CCI), measured over the baseline covariate assessment period, defined as 180 days prior to and including index date

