Appendix A

- 74.0 Classical cesarean section
- 74.1 Low cervical cesarean section
- 74.2 Extraperitoneal cesarean section
- 74.3 Removal of extratubal ectopic pregnancy
- 74.4 Cesarean section of other specified type
- 74.9 Cesarean section of unspecified type
- 74.91 Hysterotomy to terminate pregnancy
- 74.99 Other cesarean section of unspecified type
- 75.4 Manual removal of retained placenta
- 75.5 Repair of current obstetric laceration of uterus
- 75.6 Repair of other current obstetric laceration
- 75.7 Manual exploration of uterine cavity, postpartum
- 75.9 Other obstetric operations

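### As printed, the Pregnancy code list for Exclusion 12 mainly detects pregnancies that have recently ended and has no code designed to detect a woman who is pregnant at the index date

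*Combined protocol and SAP*

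**What the plan says.** Section 5.2.2 states that the criteria follow the trial as closely as possible, and says where they are defined: "Definitions for all inclusion/exclusion are provided in" Appendix A. The last step of the flowchart in Section 5.3 reads "Excluded based on Exclusion 12 - Pregnancy and Exclusion 14 - strong CYP3A4 inhibitors or strong CYP3A4 inducers", with one combined count per database.

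The Appendix A list titled Pregnancy has two parts, headed "ICD-9 Dx inpatient any position" and "ICD-9 Px inpatient any position". The diagnosis part begins with "650 Normal delivery". It goes on through complications of labour, the postpartum codes ("V24 Postpartum care and examination" and its subcodes, among them "Postpartum care and examination of lactating mother") and the outcome-of-delivery codes. The procedure part covers codes 72.0 to 75.9 and ends with "Other obstetric operations". No ICD-10 codes are printed under this title, although the VTE and major bleeding lists in the same appendix have them.

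**The concern.** An exclusion for pregnancy should remove women who are pregnant when the study drug is started. Eligibility is judged at the index date, after a 180-day baseline (Section 5.1). A delivery or postpartum code in that period shows that a pregnancy has ended. A woman who is pregnant at index and has had no labour or delivery admission matches nothing designed to find her.

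Two things are at stake. First, the study would report an eligibility criterion of the trial as emulated while the printed rule measures a different state. Second, some women who should be excluded would remain in the commercial cohorts, and the combined flowchart row would hide this, because the number removed for pregnancy is never shown.

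This differs from the absence of ICD-10 codes. Translating the same list into ICD-10 would carry the same problem forward.

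**Working it through.** **1. Content of the list, classified by printed title.**

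| Part | Group | Codes |
|---|---|---|
| Diagnoses | Delivery and complications of labour (650 to 669.94) | 10 |
| Diagnoses | Postpartum care (V24, V24.0 to V24.2) | 4 |
| Diagnoses | Outcome of delivery (V27, V27.0 to V27.7, V27.9) | 10 |
| Procedures | 72.x to 75.x | 53 |
| Total | | 77 |

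- All 77 are ICD-9 and all are restricted to inpatient claims.
- Of the 53 procedures, 51 are instrumental delivery, induction or assistance of labour, caesarean section, postpartum repair or other obstetric operations. The other two are 74.3 (removal of an extratubal ectopic pregnancy) and 74.91 (hysterotomy to terminate pregnancy), which also mark a pregnancy that has ended.
- Two procedures might be billed without a delivery: 73.91 (external version) and 75.9 (unspecified obstetric operations). They could catch a continuing pregnancy incidentally.
- Diagnosis codes for a continuing pregnancy, antenatal care or an antepartum complication: 0 of 24.

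**2. Reproducing the flowchart step (Section 5.3).** Optum 17,403 − 19 = 17,384. MarketScan (Truven) 32,489 − 44 = 32,445. Medicare 49,147 − 29 = 49,118. All three agree with the stated final cohorts.

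**3. What the flowchart reveals about size.** In the two commercial databases, Exclusions 12 and 14 together removed 19 + 44 = 63 of 17,403 + 32,489 = 49,892 patients (0.13%). The share due to pregnancy alone is not given, so 63 is only a ceiling on pregnancy removals at this step. Medicare was restricted to age 65 and over at an earlier step.

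**4. Range for women who remain (assumption).** From the Section 7 characteristics table, women number 5,965 + 3,408 = 9,373 in Optum and 11,941 + 4,704 = 16,645 in MarketScan, together 26,018. The documents give no proportion pregnant at index. If it is 0.1% to 2% of these women of all ages:

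- low: 0.001 × 26,018 = 26
- high: 0.02 × 26,018 = 520

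Against the two final cohorts (17,384 + 32,445 = 49,829), that is 0.05% to 1.0%.

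**5. Effect of removing them on pooled power.** The plan's figure is reproduced by Φ(√(events/4) × ln(2/1.12) − 1.96). With 32,998 × 13.87/1,000 = 457.7 events this gives 0.99999, as in Section 10. Suppose, at the extreme, that all 520 were in the matched set and each took a matched partner with her. Then 32,998 − 1,040 = 31,958 patients remain, with 443.3 expected events and power 0.99998.

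**The case against.** The strongest objection is that the full definition of Exclusion 12 cannot be seen. The readable part of Appendix A contains a trial summary and three code lists. Nothing is legible for the other exclusions, although the flowchart shows they were applied, and the design diagram is a figure. Exclusion 12 may have a further component or a window of its own. This stands: the point is confirmed only for the list as printed.

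Three stronger readings are tempting, and the documents do not support them.

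- A reader might infer that the pregnancy criterion is not applied at all. A narrow proxy is applied; the doubt is about which women it finds.
- A reader might infer that no pregnant woman can be caught, or that all pregnancy-related PE stays in. Codes 73.91 and 75.9 may catch a few pregnant women, and PE after an inpatient-coded delivery is what the list does remove.
- A reader might try to split the 63 into pregnancy and CYP3A4 removals by carrying the Medicare rate (29/49,147 = 0.059%) to the commercial data. Nothing supports carrying a rate from patients aged 65 and over to younger cohorts. Nor do the documents support a numerical bound on the bias in the hazard ratio.

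One might add that women who are pregnant seldom start either study drug, so few would be in the cohort. The documents neither confirm nor exclude this; it would favour the low end of the range.

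**Conclusion.** The point holds for the printed list. The flowchart names the criterion Pregnancy, the plan sends the reader to Appendix A for its definition, and the only list given there identifies mainly recent delivery or an otherwise ended pregnancy. Followed exactly, it would keep women who are pregnant at index. This is a mismatch between the rule and its purpose, rather than a missing detail.

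The consequence is minor. The number of ineligible women retained cannot be computed from the documents; 26 to 520 rests entirely on the assumed 0.1% to 2%. Medicare is practically unaffected. The effect on the primary hazard ratio is likely small, but that is a judgement and not a calculation. The conclusion would change if the unseen part of the definition contained current-pregnancy codes.

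**What to change.** Before the comparative analyses, which are still blank in Section 13:

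- Add codes for current pregnancy, antenatal care and antepartum complications to Exclusion 12, in any care setting and in both ICD versions. Assess them within the 180-day baseline up to and including the index date, and state that window beside the list.
- Keep the present delivery and postpartum codes as a separately named recent-delivery criterion.
- Report Exclusion 12 on its own flowchart row, apart from Exclusion 14.
- If a further component of Exclusion 12 already exists, print it with the list.

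The cost is a code-list change and a rerun of cohort formation, because the final cohort feeds everything after it: feasibility counts, propensity-score matching, balance tables and power. The loss of patients is small and its effect on pooled power negligible.
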